14.6.3 Primary Efficacy Endpoint

14.6.3.1 Derivation of Opioid Use Combining UDS and TLFB for a Visit

For the primary endpoint (proportion of responders for weekly opioid use over Weeks 20 to 38), overall opioid use based on the 7 daily TLFB for the prior week at a visit will be derived according to Table 6, and opioid use at a visit combining UDS and overall TLFB opioid use will be derived according to Table 7.

Table 6 Overall TLFB Opioid Use Derivation Based on Daily TLFB Results at a Given Visit

		Daily TLFB Opioids			
	All Days = Missing All Non-missing Days = Did Not Use Any Day = U				
Overall TLFB Opioids	Missing	Negative	Positive		

TLFB=TimeLine Follow Back

Table 7 Opioid Use Derivation Based on UDS and Overall TLFB Opioid Use Results at a Given Visit

		Overall TLFB Opioids		
		Missing	Negative	Positive
UDS Opioids	Missing	Missing	Negative	Positive
	Negative	Negative	Negative	Positive
	Positive	Positive	Positive	Positive

TLFB=TimeLine Follow Back; UDS=urine drug screen

14.6.3.2 Analysis

The primary objective will be evaluated for the FAS by comparing the RBP-6000 300/300-mg and the RBP-6000 300/100-mg groups on the primary endpoint:

• proportion of responders for weekly opioid use, where a responder is defined as a participant whose percentage of visits with opioid abstinence (defined as negative UDS and TLFB for opioid use) is greater than or equal to 80% over Weeks 20 to 38

(inclusive, based on 6 scheduled UDS and TLFB assessments and 4 planned random unscheduled UDS and TLFB assessments).

The percentage of visits with opioid abstinence for an individual participant will be derived as his/her number of visits with negative assessments divided by 10 (the number of the planned visits for opioid use assessments over Weeks 20 to 38), according to the composite IES. This is in fact to impute missing visits as positive. A participant with 8 or more opioid negative visits over Week 20 to 38 (i.e., greater than or equal to 80%) will be classified as a responder, otherwise as a non-responder.

A Cochran-Mantel-Haenszel (CMH) test stratified for randomisation factor will be performed to compare the 2 treatment groups on the primary endpoint.

The primary endpoint will be summarised using descriptive statistics. The ratio or difference of the responder proportions for 300 mg vs 100 mg will be presented within individual stratum and overall.

Supplementary analysis using the non-parametric randomisation-based covariance analyses (Koch 1998, Zink 2012) will be performed to account for the randomisation strata. The unadjusted ratio or difference of the responder proportions and 95% CI will be estimated.

Supplementary analysis using the non-parametric randomisation-based covariance analyses will also be performed to account for the randomisation strata and to adjust for risk factors at Screening and randomisation baseline potentially related to the primary endpoint (such as age, gender, alcohol and tobacco use, years of [injection route] opioid use, and concomitant non-opioid drug use [e.g., cocaine]). The risk-adjusted ratio or difference of the responder proportions and 95% CI will be estimated.

For the primary endpoint sensitivity estimand, the monotone missing opioid use assessment will be imputed using the logistic regression method separately within each treatment group, under a missing at random assumption. The imputation model will account for the randomisation stratification and adjust for the risk factors noted above. Intermittent missing assessments will be imputed using Markov chain Monte Carlo method to produce monotone missingness or using the worst-case outcome of the observed result immediately before and after the missing value. Fifty imputation data sets will be generated to draw statistical inference.

14.6.4 Secondary Efficacy Endpoint Analysis

Participants' percentage of days opioids were used out of days assessed (TLFB) over Weeks 10 to Week 38 (inclusive) will be based on the 7 daily TLFB for the prior week collected at the 9 scheduled and 6 random unscheduled visits. The overall opioid use percentage for an individual participant will be derived as his/her number of days of opioid use divided by the number of days with observed TLFB information, according to the while-on-treatment IES. Missing daily TLFB (monotone or intermittent) will not be imputed. For the participant who has an injection of randomised treatment but without any TLFB assessed post-randomisation (typically a rare occurrence), participant's percentage of days opioids were used will be derived based on his/her last observed TLFB assessment prior to the randomisation, i.e., the TLFB for the 7-day opioid use at the randomisation visit or the last observed TLFB after the first injection of RBP-6000 if the TLFB is also missing at the randomisation visit. A Wilcoxon ranksum (Van Elteren) test (van Elteren 1960) stratified for randomisation factor will be performed to compare the 2 treatment groups. The endpoint will be summarised using descriptive statistics. The cumulative distribution function by treatment group within individual stratum and overall will be graphically explored. The ratio or difference of the treatment group means for 300 mg vs 100 mg will be presented within individual stratum and overall. Supplementary analysis using the non-parametric randomisation based covariance analyses (Koch 1998, Zink 2012) will be performed to account for the randomisation strata. The unadjusted ratio or difference of the treatment group means and 95% CI will be estimated. Supplementary analysis using the non-parametric randomisation based covariance analyses will also be performed to account for the randomisation strata and to adjust for risk factors at Screening and randomisation baseline potentially related to the endpoint (such as age, gender, alcohol and tobacco use, years of [injection route] opioid use, and concomitant nonopioid drug use [e.g., cocaine]). The risk adjusted ratio or difference of the treatment group means and 95% CI will be estimated.

Proportion of responders for weekly opioid use, where a responder is defined as a participant whose percentage of visits with opioid abstinence (as measured via negative UDS and TLFB for the prior week) is greater than or equal to 80% over Weeks 10 to 38 (inclusive), will be analysed in the same manner as the primary endpoint. The opioid abstinence percentage for an individual participant will be derived as his/her number of

visits with negative assessments divided by 15. A participant with 12 or more opioid negative visits over Week 10 to 38 (i.e., greater than or equal to 80%) will be classified as a responder, otherwise as a non-responder.

Participants' percentage of visits with opioid abstinence (defined as negative UDS and TLFB for opioid use) over Weeks 10 to 38 (inclusive, based on 9 scheduled UDS and TLFB assessments and 6 planned random unscheduled UDS and TLFB assessments). will use the composite IES to impute missing visits as positive. A Wilcoxon rank-sum (Van Elteren) test (van Elteren 1960) stratified for randomisation factor will be performed to compare the 2 treatment groups. The cumulative distribution function by treatment group within individual stratum and overall will be graphically explored and will compare various cut points for classifying a responder. The difference and ratio of responder rates for the 2 treatment groups will be described under the various cut points.

The responders for weekly opioid use will be based on participants' percentage of visits with opioid abstinence being greater than or equal to 80% for the last 5 visits planned for UDS and TLFB assessment over Week 30 to Week 38, using the composite IES to impute missing visits as positive. The opioid abstinence percentage for an individual participant will be derived as his/her number of visits with negative assessments divided by 5. A participant with 4 or more opioid negative visits over Week 30 to 38 (i.e., greater than or equal to 80%) will be classified as a responder, otherwise as a non-responder.

The responders for the daily opioid use will be based on the 7 daily TLFBs for the prior week collected at the last 5 observed visits post randomisation. The opioid use percentage for an individual participant will be derived as his/her number of days opioids were used divided by the number of days with observed TLFB information at those 5 visits post randomisation, according to the while-on-treatment IES with no imputation for missing data. For participants who have less than 5 visits with observed TLFB post randomisation, all available daily TLFB will be used to derive the opioid use percentage. A participant with 20% or less opioid use percentage will be classified as a responder, otherwise as a non-responder. The participant without observed daily TLFB will also be classified as non-responder.

The proportion of responders (for weekly and daily opioid use) will be compared between treatment groups using the unadjusted non-parametric ANCOVA approach accounting for randomisation stratification described in Section 14.6.3. The difference between treatment groups will be estimated with 95% CI.

The participants' percentage of visits with opioid abstinence (defined as negative UDS and TLFB for opioids use) overall (Week 2 to 38 inclusive) will be analysed in the same manner as the primary endpoint. In addition, this endpoint will be graphically presented using the cumulative distribution function.

The 2 secondary endpoints (participants' percentage of days opioids were used out of days assessed [TLFB] overall [Week 2 to 38 inclusive] and participants' percentage of days opioids were used via the injection route out of days assessed [TLFB] overall [Week 10 to 38 inclusive]) will be analysed in the same manner as secondary endpoint 2, except the analysis population for "used opioids via the injection route" will be those participants who use opioids via the injection route for an average of 5 or more days per week in the last 4 weeks prior to Screening sub-population of the FAS.

The average number of times opioids were used per week (TLFB) for a given visit within a treatment group will be based on the 7 daily TLFBs for the prior week collected at that visit, and calculated as the number of times opioids were used divided by the number of days with observed TLFB information for all participants within the group for that visit, then times 7. The endpoint will utilise a while-on-treatment IES with no imputation for missing data. The average value for each treatment group will be summarised by visit from Screening to Week 38 for overall and within individual randomisation stratum; the difference between treatment groups will be estimated with a 95% CI for each visit.

[figure not shown]
The change in participants' number of times opioids were used per week from Screening or randomisation baseline to each visit will be based on the 7 daily TLFB for the prior week collected at that visit. A "while-on-treatment" strategy will be used to address IEs, in that only the participants with complete 7 daily TLFB information for a given visit will be analysed for that visit. The mean change value or percentage change value from Screening or randomisation baseline for each treatment group will be summarised by visit from Screening or randomisation baseline to Week 38 for overall and within individual randomisation stratum; the difference between treatment groups will be estimated with a 95% CI for each visit. As an alternative approach to handle missing data, a supplemental analysis will include participants with complete or partial daily TLFB information at the visit. The participants with partial daily TLFB information at a given visit will be imputed as the number of times opioid were used divided by the number of days with observed TLFB information times 7 for that visit.

The proportion of participants abstinent (defined as negative UDS and TLFB for opioid use) for a given visit within a treatment group will be calculated as the number of participants abstinent (derived according to Table 6 and Table 7) divided by the number of participants with observed opioid use assessment for that visit. The average number of days opioids were used per week (TLFB) for a given visit within a treatment group will be calculated as number of days opioid were used divided by the number of days with observed TLFB information for all participants within the group for that visit, then times 7. Both endpoints will utilise a while-on-treatment IES with no imputation for missing data. The proportion or the average value for each treatment group will be summarised by visit from Screening to Week 38 for overall and within individual randomisation stratum; the difference between treatment groups will be estimated with a 95% CI for each visit.

The treatment retention since randomisation will be derived as the number of days from randomisation until the date of discontinuation. Participants who complete the study will be censored administratively at the EOT visit. The endpoint will be presented by treatment group for overall and within individual randomisation stratum using a Kaplan-Meier curve. Intercurrent events and missing data are not applicable for this endpoint.

The proportion of participants who complete the last scheduled injection of RBP-6000 at Week 34 will be compared between treatment groups using the unadjusted non-parametric ANCOVA approach accounting for randomisation stratification described in Section 14.6.3. The difference between treatment groups will be estimated with 95% CI. Intercurrent events and missing data are not applicable for this endpoint.

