Primary Efficacy Endpoint Sensitivity	As primary	As primary	Composite strategy: The monotone missing opioid usage assessment will be imputed using logistic regression method separately within each treatment group, under a missing at random assumption. The imputation model will include the RF and baseline factors used for the non-parametric ANCOVA. Fifty imputation data sets will be generated to draw statistical inference. Intermittent missing assessments will be imputed using Markov chain Monte Carlo method to produce monotone missingness or using the worst-case outcome of the observed result immediately before and after the missing value.	As primary for each imputed dataset

Table 5 Primary and Secondary Estimands

			Estimand Attributes	
Statistical Category	Variable/ Endpoint	Population	IES	PLS (Analysis)
Secondary Efficacy Endpoint 1	Participants' percentage of days opioids were used out of days assessed (TLFB) over Weeks 10 to Week 38 (inclusive)	As primary	While-on-treatment strategy Missing daily TLFB (monotone or intermittent) will not be imputed. For the participant who has an injection of randomised treatment but without any TLFB assessed post-randomisation (typically a rare occurrence), participant's percentage of days opioids were used will be derived based on his/her last observed TLFB prior to the randomisation, i.e., the TLFB for 7-day opioid use at the randomisation visit or the last observed TLFB after the first injection of RBP-6000 if the TLFB is also missing at the randomisation visit.	Wilcoxon rank-sum test stratified for RF to provide the unadjusted treatment group comparison Ratio/difference of the treatment group means (300 mg vs. 100 mg) will be estimated using non-parametric ANCOVA accounting for randomisation stratification to provide the 95% CI for unadjusted estimation Non-parametric ANCOVA to account for randomisation stratification and to adjust for factors at Screening or randomisation baseline potentially related to the endpoint (age, gender, alcohol and tobacco use, years of [injection route] opioid use, and concomitant non-opioid drug use [e.g., cocaine]) to provide the 95% CI for risk-adjusted estimation

 Table 5
 Primary and Secondary Estimands

	Estimand Attributes					
Statistical	Variable/				PLS	
Category	Endpoint	Population	IES		(Analysis)	

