Secondary Efficacy Endpoint 2	Proportion of responders for weekly opioid use, where a responder is defined as a participant whose percentage of visits with opioid abstinence (as measured via negative UDS and TLFB for the prior week) is greater than or equal to 80% over Weeks 10 to 38 (inclusive)	As primary	As primary	As j	primary	

Table 5 Primary and Secondary Estimands

			Estimand Attributes	
Statistical	Variable/		_	PLS
Category	Endpoint	Population	IES	(Analysis)
			300-mg maintenance doses of RBP-6000 ado use opioids via an injection route and/or us	ministered every 4 weeks on treatment outcomes se high doses of opioids
Secondary 3	Percentage of visits with opioid abstinence (defined as negative UDS and TLFB for the prior week) over Weeks 10 to Week 38 (inclusive)	As primary	As primary	As secondary 1
Secondary 4	Proportion of responders for weekly opioid use, defined as - participants' percentage of visits with opioid abstinence being greater than or equal to 80% (for the last 5 visits planned for UDS and TLFB	As primary	Composite strategy: impute missing visits as positive	The proportion of responders will be compared between treatment groups using the unadjusted non-parametric ANCOVA approach accounting for randomisation stratification described in Section 14.6.3.2. The ratio/difference between treatment groups will be estimated with 95% CI.

Table 5 Primary and Secondary Estimands

			Estimand Attributes	
Statistical	Variable/			PLS
Category	Endpoint	Population	IES	(Analysis)
	assessment over Week 30 to 38)			

Table 5 Primary and Secondary Estimands

			Estimand Attributes	
Statistical Category	Variable/ Endpoint	Population	IES	PLS (Analysis)
Secondary 5	Proportion of responders for daily opioid use, defined as participants' percentage of days opioids were used out of days assessed (TLFB) being less than or equal to 20% for participants' last 5 visits with observed TLFB post randomisation.	As primary	While-on-treatment Missing data will not be imputed	As secondary 4
Secondary 6	Participants' percentage of visits with opioid abstinence (defined as negative UDS and TLFB for opioid use) overall (Week 2 to 38 inclusive)	As primary	As primary	As primary

Table 5 Primary and Secondary Estimands

			Estimand Attributes	
Statistical Category	Variable/ Endpoint	Population	IES	PLS (Analysis)
Secondary 7	Participants' percentage of days opioids were used out of days assessed (TLFB) overall (Week 2 to 38 inclusive)	As primary	As secondary 1	As secondary 1

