Secondary 8	Participants' percentage of days opioids were used via the injection route out of days assessed (TLFB) overall (Week 10 to 38 inclusive)	Analysis population: The participants who use opioids via the injection route for an average of ≥5 days per week in the last 4 weeks prior to Screening sub- population of the FAS	As secondary 1	As secondary 1
Secondary 9	Average number of times opioids were used per week (TLFB) by visit	As primary	While-on-treatment strategy Missing daily TLFB (monotone or intermittent) will not be imputed.	The average number of times opioids were used per week (TLFB) for each treatment group will be summarised by visit from Screening to Week 38 for overall and within individual randomisation stratum; the difference between treatment groups will be estimated with a 95% CI for each visit.

 Table 5
 Primary and Secondary Estimands

			Estimand Attributes	
Statistical Category	Variable/ Endpoint	Population	IES	PLS (Analysis)
Secondary 10	Change in participants' number of times opioids were used per week from Screening or randomisation baseline to each visit	As primary	While-on-treatment strategy Only the participants with complete 7 daily TLFB information for a given visit will be analysed for that visit. As an alternative approach to handle missing data, a supplemental analysis will include participants with complete or partial daily TLFB information at the visit. The participants with partial daily TLFB information at a given visit will be imputed as number of times used opioid divided by the number of days with observed TLFB information times 7 for that visit.	The mean change value or percentage change value from Screening or randomisation baseline for each treatment group will be summarised by visit from Screening or randomisation baseline to Week 38 for overall and within individual randomisation stratum; the difference between treatment groups will be estimated with a 95% CI for each visit.
Secondary 11	Proportion of participants abstinent (defined as negative UDS and TLFB for opioid use) by visit.	As primary	While-on-treatment strategy Visit with missing opioid use assessments will not be imputed.	Proportion of participants abstinent will be estimated with 95% CI by visit for individual treatment groups from Screening to Week 38. The difference between the treatment groups will be estimated with 95% CI by visit
Secondary	Average number of	As primary	While-on-treatment strategy	The average number of days opioids were used

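### Section 14.6.4 points Secondary 7 and 8 to the wrong model analysis, and gives Secondary 6, a percentage, a responder analysis with no divisor, cut-off or scores

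*Protocol*

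**What the plan says.** **Secondary 7 and 8.** These are each participant's percentage of assessed TLFB days with opioid use (Weeks 2 to 38), and with use by injection (Weeks 10 to 38, in the injecting subpopulation). Protocol Section 14.6.4 says they "will be analysed in the same manner as secondary endpoint 2, except the analysis population" is restricted for the injection-route endpoint. Table 5 in Section 14.6.2 refers both back to secondary 1, in the intercurrent-event column and in the analysis column. For secondary 1 the test is "Wilcoxon rank-sum test stratified for RF to provide the unadjusted treatment group comparison", and the missing-data rule is "Missing daily TLFB (monotone or intermittent) will not be imputed".

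The numbering is not in doubt. The Table 5 row labelled "Secondary Efficacy Endpoint 2" is the Weeks 10 to 38 responder proportion, and Section 3.2 also lists it second.

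**Secondary 6.** Table 5 defines it as "Participants' percentage of visits with opioid abstinence (defined as negative UDS and TLFB for opioid use) overall (Week 2 to 38 inclusive"), with no threshold. Section 14.6.4 says the endpoint "overall (Week 2 to 38 inclusive) will be analysed in the same manner as the primary endpoint", and Table 5 agrees. The primary analysis in Section 14.6.3.2 is a stratified CMH test on a yes/no responder, with divisor 10 and cut-off 8, both tied to Weeks 20 to 38. Section 14.6.4 also plans a cumulative distribution plot for Secondary 6.

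**The concern.** For Secondary 7 and 8, two parts of the protocol prescribe different missing-data strategies and different tests. The rule in the analysis text is built on counts of negative visits, so it cannot be executed on a percentage of days used.

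For Secondary 6, the instruction to follow the primary can be read in at least three ways:
- a responder CMH test at some carried-over cut-off;
- a CMH mean-score test on the percentage itself;
- a CMH mean-score test on within-stratum ranks, which is the van Elteren test when ranks are standardised by stratum size.

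The responder reading discards most of the information. At a cut-off of 19, a participant with 18 of 23 negative visits counts the same as one with none. Section 14.6.7 applies no multiplicity procedure and tests each endpoint at a nominal 5%. Fixing the test in advance is therefore the main safeguard against choosing among these readings once results are known.

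**Working it through.** **Inputs.** Visits with both UDS and TLFB come from Appendices 22.4 to 22.6: Weeks 2 to 10 weekly, then every two weeks from Week 12 to Week 38. The random visits fall at Weeks 12, 16, 20, 24, 28 and 32. The 80% rule comes from Section 14.6.3.2.

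**Reproducing the plan's own divisors and cut-offs** (cut-off = 0.80 × number of visits, rounded up):
- Weeks 20 to 38: 6 scheduled + 4 random = 10; cut-off 8. Matches Section 14.6.3.2.
- Weeks 10 to 38: 9 scheduled + 6 random = 15; cut-off 12. Matches Section 14.6.4.
- Weeks 30 to 38: 5 visits; cut-off 4. Matches Section 14.6.4.

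**The same count for Secondary 6.** Weeks 2 to 10 give 9 visits and Weeks 12 to 38 give 14, so 9 + 14 = 23. Carrying over the 80% rule, 0.80 × 23 = 18.4, hence 19 of 23 (82.6%), allowing 23 − 19 = 4 positive or missed visits. Neither 23 nor 19 appears in the documents.

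**Secondary 7 and 8, side by side:**

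| | Secondary 1 (Table 5's reference) | Secondary 2 (Section 14.6.4's reference) |
|---|---|---|
| Data | TLFB days used ÷ days observed | Negative visits ÷ 15 |
| Missing | Not imputed | Counted as positive |
| Form | Percentage | Responder if 12 or more |
| Test | Stratified Wilcoxon | Stratified CMH |

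Consider a participant with no opioid use who leaves after Week 26. Under the secondary 1 rule the score is 0% of days used, the best possible. Under the secondary 2 rule the negative visits at Weeks 10 to 26 number 9, and 9/15 = 60%, a non-responder.

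**How much the reading of Secondary 6 matters.** The documents give no inputs for this, so the simulation is illustrative. Assumptions:
- 390 participants (the planned number) randomised 1:1 in four strata of 30, 25, 25 and 20%.
- Participant log-odds of a negative visit are normal with mean 0 or −0.5, stratum shifts of ±0.5 and SD 1.5 to 3.5.
- Exponential discontinuation after Week 6 reaches 30% or 45% by Week 38.
- The treatment log-odds effect is 0.4 to 0.8 from Week 7.
- Missing visits are positive; 2,000 trials per scenario; two-sided 5%.

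Results over six non-null scenarios:
- responder CMH at 19 of 23: power 16.2% to 31.1%;
- stratified van Elteren: power 24.5% to 56.5%;
- opposite verdicts between these two: 19.6% to 33.7% of trials;
- opposite verdicts between the mean-score CMH on the raw percentage and van Elteren: 3.8% to 6.4%.

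With no effect, the rejection rates were 4.8% (responder), 5.0% (mean score) and 4.7% (van Elteren). Monte Carlo error at 5% is √(0.05 × 0.95 / 2000) = 0.5 points, so all three hold their level.

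A separate simulation under similar assumed inputs gave power of about 15% to 20% for the responder test and 29% to 35% for van Elteren, with opposite verdicts in about 21% to 27% of trials.

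**The case against.** The best defence is that little is really open. For Secondary 7 and 8 the text rule cannot be executed, Table 5 is clear in both columns, and Section 14.6.4 spells out the secondary 1 method, so this is a numbering slip. That is a fair description of its cause. It remains a wrong instruction in the analysis section and needs correcting.

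For Secondary 6, text and table agree, so there is no contradiction. The missing-data rule is settled (missing counts as positive), and the divisor follows from the primary's principle of dividing by planned visits. The non-parametric ANCOVA part of the primary analysis could run on a mean percentage. All of that stands and narrows the gap to the CMH component, which still needs a cut-off or scores.

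The 19-of-23 rule is also a construction. The absence of a threshold and the planned distribution plot both favour a percentage reading, and the two percentage-based readings differ little. The 20% to 34% disagreement therefore describes the consequence of the responder reading, not an expected error. Much of it reflects the power gap under assumed inputs, since two tests must disagree at least as often as their powers differ.

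Finally, moving Secondary 6 to van Elteren changes the analysis named in two places. That is true. But it is the test the protocol already assigns to the same variable over Weeks 10 to 38 (Secondary 3).

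**Conclusion.** Both points hold on the protocol text. Secondary 7 and 8 have conflicting rules, and the one in Section 14.6.4 cannot be applied. No numerical effect can be given, because that rule cannot be computed from days used. Secondary 6 is under-specified: a percentage is sent to a responder analysis without the quantities needed to run its test. The choice that matters is responder against percentage; the two percentage-based tests rarely disagreed. The visit counts follow from the schedules, whereas the simulated percentages rest wholly on assumed inputs.

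The consequence is limited to three of the 14 secondary endpoints, all tested nominally, and the primary analysis is untouched. This should be corrected, but it does not threaten the trial's main conclusion. The supplied SAP covers only the induction sub-study, so a main-study SAP may already contain the answer.

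**What to change.** - **Secondary 7 and 8:** in Section 14.6.4, change the reference from secondary endpoint 2 to secondary endpoint 1, matching Table 5.
- **Secondary 6:** in Section 14.6.4 and in the Table 5 row, refer the analysis to secondary 3. State it as negative visits divided by 23, missing visits positive, stratified van Elteren test, and non-parametric ANCOVA on the mean. Keep the endpoint definition, the window and the distribution plot. If a responder version is also wanted, give it its own stated cut-off.

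The cost is one cross-reference, one sentence and one table cell. No new data are needed and no endpoint changes, although the analysis named for Secondary 6 does. Protocol Section 17 requires a formal amendment, submitted to the IRB/IEC, for a permanent protocol change. If none is otherwise planned, the main-study SAP is the cheaper place, since Section 14.1 lets it add analysis detail and record deviations. Either way, the change should be dated before unblinding.

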5 POPULATION

5.1 Number of Participants

It is planned for approximately 390 participants to be randomised immediately prior to their third injection, 4 weeks after their second 300-mg dose of RBP-6000, at a 1:1 ratio (195 per group) to receive either 300 mg RBP-6000 or 100 mg RBP-6000 for subsequent monthly doses.

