14.6.7 Multiplicity

There will be no multiplicity procedure applied across primary, secondary, and exploratory endpoints. Where statistical testing is performed, significance will be assessed at a nominal 2-sided 5% alpha-level.

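### Secondary 10 names no baseline adjustment for its by-visit difference in change in weekly opioid use, a free precision gain left unused

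*Protocol*

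**What the plan says.** Table 5 in Protocol 14.6.2 defines Secondary 10 as "Change in participants' number of times opioids were used per week from Screening or randomisation baseline to each visit". For the arm comparison it says that "the difference between treatment groups will be estimated with a 95% CI for each visit". Section 14.6.4 repeats this and describes the reported quantity: "The mean change value or percentage change value from Screening or randomisation baseline for each treatment group will be summarised by visit". The summaries are given "for overall and within individual randomisation stratum". The main analysis is restricted to complete weeks: "only the participants with complete 7 daily TLFB information for a given visit will be analysed for that visit". No model, covariate or stratum-combining estimator is named for the overall difference.

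Elsewhere the protocol does name one. For the primary endpoint, 14.6.3.2 states: "Supplementary analysis using the non-parametric randomisation-based covariance analyses (Koch 1998, Zink 2012) will be performed to account for the randomisation strata". It then adds a version adjusted for risk factors. Secondary 1 gets both versions. Secondary 4, 5 and 14 get the version that uses strata only.

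Two items are left for later. Section 14.6.1 says the baseline for each endpoint will be fixed in the protocol or the SAP, and 14.1 leaves further analysis detail to the SAP. The SAP supplied covers only the induction sub-study (SAP section 1) and is silent on Secondary 10.

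**The concern.** A change score subtracts the whole baseline value, whatever the true relation between baseline and follow-up. If that relation is weaker than one-for-one, the subtraction adds baseline noise to the comparison.

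This could matter more than usual here. Entry requires opioid use on an average of at least 5 days a week (Protocol 5.2). The TLFB supplement counts how many times a day opioids were used (8.3.2), so the Screening count has no natural ceiling. Use on treatment should be lower. A Screening SD larger than the on-treatment SD is therefore plausible, though not documented.

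Frequency of use is the example of harm reduction given in the secondary objective (2.2). At stake is the width of the interval around the dose comparison at each visit.

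**Working it through.** **Inputs from the documents**
- Protocol 5.1 randomises "at a 1:1 ratio (195 per group) to receive either 300 mg RBP-6000 or 100 mg RBP-6000". As a check, 390/(1 - 0.20) = 487.5, so 488 must be inducted at 20% loss. The sub-study appendix states 489, which agrees closely.
- The complete-week rule makes 195 per arm the most that any visit can have.
- No SD, correlation, effect size or power is given for Secondary 10, so there is no plan figure to reproduce for the endpoint itself.

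**Assumed inputs**
- k = SD(baseline)/SD(visit)
- rho = correlation between baseline and visit count

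**Formulas** (per-arm variance in units of the visit variance, large samples)
- Raw change: k² + 1 - 2·rho·k
- Baseline-adjusted: 1 - rho²
- Excess of raw change: (k - rho)². This is never negative, and is zero only when k = rho, that is, when the regression slope rho/k equals 1.
- CI width ratio: square root of the variance ratio
- Sample size that 195 per arm is worth: 195 divided by the variance ratio

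**Results**

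| k | rho | Raw change | Adjusted | Variance ratio | CI wider by | 195 per arm worth |
|---|---|---|---|---|---|---|
| 1 | 0.3 | 1.40 | 0.91 | 1.54 | 24% | 127 |
| 1 | 0.5 | 1.00 | 0.75 | 1.33 | 15% | 146 |
| 1 | 0.7 | 0.60 | 0.51 | 1.18 | 8% | 166 |
| 1 | 0.9 | 0.20 | 0.19 | 1.05 | 3% | 185 |
| 2 | 0.2 | 4.20 | 0.96 | 4.38 | 109% | 45 |
| 2 | 0.5 | 3.00 | 0.75 | 4.00 | 100% | 49 |
| 2 | 0.7 | 2.20 | 0.51 | 4.31 | 108% | 45 |
| 0.5 | 0.5 | 0.75 | 0.75 | 1.00 | 0% | 195 |

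Raw change is noisier than the visit count alone when k² + 1 - 2·rho·k > 1, that is, when rho < k/2. With k = 1 that means any rho below 0.5. With k = 2 it means any rho below 1.

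**Chance baseline imbalance.** If the arms differ by d at baseline, the net conditional error in the change-score difference is (1 - slope)·d in size. At k = 2 and rho = 0.5 the slope is 0.5/2 = 0.25, so 75% of the imbalance remains.

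**Simulation.** Two assumed scenarios were run with skewed counts and stratified 1:1 randomisation, 4,000 trials each. The simulated Screening SD was more than twice the visit SD. Mean 95% CI widths were:
- Change from Screening: 6.2 and 6.7, against 2.6 and 2.7 when adjusted for Screening.
- Change from Week 6: 2.76 and 2.06, against 2.36 and 1.88 when adjusted for Week 6.
- Adding only the strata to the Week 6 change score: 2.76 to 2.67 and 2.06 to 2.02, a narrowing of 2-3%.

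The gain comes from the baseline covariate, and it is much larger for Screening than for Week 6.

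**The case against.** The strongest reply is that the protocol is silent on the estimator; it does not reject adjustment. It never calls the difference raw or unadjusted, and it leaves detail to a SAP. The main-study SAP is not among the documents. This stands: the claim can only be that no adjustment is named.

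Second, Secondary 10 is not an outlier. Secondary 9, 11 and 12 get the same by-visit treatment, so these endpoints form a consistent descriptive group. Secondary 9 already compares weekly times used without subtracting baseline, and Secondary 1, 7 and 8 also carry frequency of use. The secondary objective therefore does not depend on Secondary 10. This stands and limits the importance.

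Third, the precedent is partial. The analyses of Secondary 4, 5 and 14 take strata but no covariates. The risk factors listed for the primary endpoint and Secondary 1 do not include baseline frequency of use, though the list is open-ended. The method is the protocol's own; the covariate would be new.

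Three stronger readings are tempting, and the documents do not support them:
- A reader might infer that the comparison is biased by baseline imbalance. It is not: such an imbalance is sampling error that the CI covers.
- A reader might infer that the strata are ignored. They are used to present results, though not to combine them, and in simulation combining them gained little.
- A reader might turn the wider interval into lost power. No test is named for Secondary 10, and 14.6.7 says that "significance will be assessed at a nominal 2-sided 5% alpha-level" only where testing is performed. Any power figure would describe an analysis that is not planned.

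**Conclusion.** The point holds as a matter of precision. As written, the overall by-visit difference has no named adjustment for the baseline that defines it, and in large samples adjusting for that baseline cannot make the estimate less precise.

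The size depends on assumed SDs and correlations. The loss is likely to be large for change from Screening, if Screening counts vary more than on-treatment counts. It may be only 3-8% in CI width for change from Week 6, if SDs are equal and the correlation is 0.7 to 0.9. It vanishes if the regression slope is 1. A higher Screening mean does not by itself establish a larger Screening SD, so the twofold figure remains an assumption.

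The algebra covers absolute change only, not the percentage-change option. The complete-week, while-on-treatment restriction is a separate matter that adjustment does not resolve. This is a desirable refinement and does not threaten any conclusion of the trial.

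**What to change.** In Protocol 14.6.4 and the Secondary 10 row of Table 5 (or in the main-study SAP, if it is still open):
- Estimate the per-visit difference in absolute change with the non-parametric randomisation-based ANCOVA cited in 14.6.3.2. Stratify by injection route at Screening and Week 6 opioid UDS, and use the matching baseline weekly count as the covariate.
- If both baselines are kept, run one analysis for Screening and one for Week 6, each with its own covariate.
- Keep raw mean changes, and any percentage change, as description only. Percentage change is undefined for a participant with no use in the baseline week, which can occur at Week 6.
- Apply the same estimator to the supplemental analysis that scales up partial weeks.

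The cost is one covariate in a method already planned for other endpoints. The TLFB is already scheduled at Screening and Week 6. A change score already needs the baseline count, so no further participants are lost.
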